#### *D.4.1.2 Physical Activity by Questionnaire*

All participants will have AEE assessed by questionnaire, in their own language, using the Global Physical Activity Questionnaire version 2 (GPAQ) [164]. The GPAQ was developed by the World Health Organization (WHO) as part of the WHO STEPwise approach to chronic disease risk-factor surveillance (STEPS manual available online at <http://www.who.int/chp/steps/manual/en/>) [165] to produce reliable and valid estimates of physical activity for use in culturally diverse populations in developing countries. Approximately 50 developing countries are currently using the GPAQ for physical activity data collection. The main outcome variables are: a categorical variable of total physical activity (high, moderate and low) and a continuous variable of total physical activity within each domain of work, transport and leisure.

#### **D.4.2 Body Composition**

##### *D.4.2.2 Bioelectrical Impedance Analysis*

Body composition will also be assessed in all participants using BIA. BIA measures the impedance to the flow of an applied mild alternating current by body tissues. The measured impedance of body tissues can be used to calculate total body water, from which fat-free mass and fat mass can be calculated [170]. BIA is a relatively inexpensive method to estimate body composition in populations.

The participants will be placed in the supine position with limbs abducted. Current-supplying electrodes will be placed on the dorsal surfaces of the right hand and foot at the metacarpals and metatarsals, respectively. Detection electrodes will be placed at the pisiform prominence of the right wrist and the anterior surface of the true ankle joint [170]. The single-frequency instrument (BIA Quantum, RJL Systems, Clinton Township, MI) will be attached to electrodes and generate an excitation current of 800  $\mu$ A at 50kHz.

The investigators on this application have extensive experience in the application of BIA in field situations and have developed equations for use in Nigerian, Jamaican and African-American adult and child populations [112, 119]. Unless evidence from the ID analyses, described above, indicates a need for the development of separate equations for the other African sites, we propose to use the pre-existing validated BIA equations. The ID data will be used to calibrate BIA for change in body composition within individuals over the 2-year follow-up.

##### *D.4.2.3 Dual X-ray Absorptiometry (DXA)*

Participants will undergo a bone mineral density measurement using dual x-ray absorptiometry (DXA). The bone scan takes approximately 30 minutes and will require the participant to remove all metal jewelry and piercings. To ensure women are not unknowingly pregnant, they will be asked the date of their last period, given a pregnancy test and will be excluded if they are pregnant. Individuals with pacemakers will be excluded.

#### D.4.3 Anthropometrics

At the initial clinic visit, height, weight, waist and hip circumferences, and blood pressure will be measured. Weight of the participant will be measured without shoes and dressed in light clothing to the nearest 0.1 kg using a standard balance (Health-o-meter, Bridgeview, IL). Height will be measured using a stadiometer without shoes and head held in the Frankfort plane to the nearest 0.1 cm. Waist circumference will be measured to the nearest 0.1 cm at the umbilicus. Hip circumference will be measured to the nearest 0.1 cm at the point of maximum extension of the buttocks. For both waist and hip circumferences, repeat measures will be taken. If two measurements differ by more than 0.5 cm, a third measurement will be taken.

#### D.4.4 Dietary Intake

Dietary intake is not the primary focus of this application, however, we recognize that estimates of EI and diet composition data may improve the analysis of energy balance. We are cognizant of the challenges involved in comparing dietary intake across multiple populations [69-72, 171]. Using both INTER-MAP and EPIC as models, we will attempt to collect and measure dietary intake, with appropriate quality control measures, in these 5 populations at varying stages of the epidemiologic transition. We regard this as an additional contribution to the long-term effort to collect international comparative diet data for epidemiologic studies, and one that will continue to be refined.

The dietary component of this project will be directed by [name] at the Medical Research Council (MRC) of South Africa. [name] has extensive experience in assessing the diets of multiple countries in sub-Saharan Africa [145, 172-175], and has developed a system for portion size estimation in collaboration with a MRC colleague which has been utilized in South Africa and Kenya (DAEK, [176]). Quality control measures will include centralized training for all interviewers led by [name] (cf. section D.5); training will include discussion and documentation of site-specific prompts and portion sizes for the dietary interviews, decision on standardized coding of the recalls, and methods for the audiotape recording of the interviews. We will use the five indicators suggested by INTERMAP to assess performance quality: evaluation of audiotapes, number of foods coded, coding error rates, duration of the recall and total energy intake (kcal or kJ) per recall [171]. [name] and/or a post-doctoral fellow will travel to each during pilot training to insure proper implementation of the protocol. The Nutrient Data System for Research (NDSR; U. Minnesota, Minneapolis, MN) will be modified and utilized for nutrient analysis. The first year will be spent setting up the NDSR to accommodate those foods/recipes local to each site using the currently available site-specific nutrient databases and the previously collected 24-hour recall data (cf. Table 4). In the 3 African countries, this will not be an excessive number of foods – eg, in Nigeria only 75 different foods/food mixtures mentioned in over 200 collected recalls.

In brief, each participant will complete at least two 24-hour recalls using the multiple pass method, one at the initial baseline examination and the second when the activity monitor is collected. The DLW subset of participants will have 3 dietary recalls - the third recall conducted at the midpoint urine sample collection. With these multiple recalls, usual intake distributions of nutrients can be estimated (cf. Section D.7.1.3; [177-179]. At each site, the 24-hour recalls will be collected by trained interviewers using pen and paper; an audiotape recording will also be made of the recall interviews and used to augment the written record where necessary, as well as for quality control. The 24-hour recalls will be scanned and sent via e-mail to the MRC in South Africa where data entry and analysis will take place. Endpoints of interest will be total EI and macronutrient composition (ie, % kcals from fat, carbohydrate and protein), as well as indicators of intake of processed foods (ie, # of sweetened beverages, pre-packaged foods and restaurant fast foods per day) and of intake of fruits, vegetables and site-specific staples (cf. Table 4). While we recognize the importance of micronutrients for

overall health and well-being of individuals, many nutrient databases are lacking sufficient data on local food micronutrient content.

#### D.4.4 Blood Pressure

Blood pressure will be measured using the protocol and training procedures developed for our ongoing international hypertension studies. Blood pressure will be measured using the Omron Automatic Digital Blood Pressure Monitor (model HEM-747lc, Omron Healthcare, Bannockburn, IL, USA). With the antecubital fossa at heart level, three pulse and blood pressure readings will be taken.

#### D.4.6 Mouse model

Following the identification of obesity-related fecal/oral microbiome in the METS participant samples, and as a proof of research concept, fecal/oral microbiome samples, collected in D.4.5, will be transplanted in sterile mice, who will be evaluated for the development of adiposity and type 2 diabetes. All the mice work will be preformed at Division of Endocrinology, Metabolism and Molecular Medicine, Northwestern University, under the supervision of [name]. Specifically, male mice will have their gut microbiota ablated by oral gavage of ampicillin over a 2 week period. After the final oral antibiotic dose, mice will have the fecal transfer, once a week for 4 weeks. At the end of each week, mice will receive an intraperitoneal glucose tolerance test, in addition to adiposity measurements. Mice will be sacrificed after 4 weeks for tissue collection. This proof of concept study has been approved by the Northwestern University Institutional Animal Care and Use Committee

#### D.4.7 Skin Pigmentation

Participants will have their skin pigmentation measured by a handheld DSM II ColorMeter at the inner upper right and left arms.

### D.5 Centralized Training of Staff and Certification

In the first 6 months, after protocols and procedures have been approved by the investigators, a centralized training session for all staff will be held in Chicago. Over the course of one week, all staff will be

trained by previously certified project coordinators on procedures to be used for the study. All methods have been employed in previous studies at the coordinating institution, Loyola University. The project coordinator from Loyola will be responsible for the training and certification on the DLW and accelerometer methods, and anthropometric, body composition and blood pressure measurements. [name] and her coordinator will be responsible for training and certification on the dietary intake methods.

## **D.6 International Transport of Samples**

International shipment of biological samples has become complicated by security precautions. Based on prior experience, it has been decided that samples to the US, i.e., DLW and plasma samples, will be carried by investigators as they travel to/from the annual investigator meeting if there is evidence of problems with shipping, e.g., from Jamaica. After appropriate aliquotting, the samples will be packed on dry ice in insulated shipping containers and checked as baggage. In the case of Nigeria and South Africa, no such problems have arisen to date; therefore, samples will be shipped directly on dry ice by an express shipping company. For DLW samples transported to Loyola, they will subsequently be re-packed on dry ice and shipped overnight to the University of Wisconsin in Madison, Stable Isotope Core Laboratory. Duplicates of all samples will be stored in the laboratories of origin.

## **D.7 Statistical Considerations**

Statistical analyses will be supervised by [name]. He will generate reports on accrual, missing data items, and alerts (if any). With the assistance of the PI and the programmer, he will undertake the analyses outlined below. A data coordinating center (DCC) will be established to manage and administer data transfers between sites. Data quality control and assurance processes will be put in place by the DCC.

### **D.7.1 Statistical Analysis**

In the initial stage of the analysis, a complete set of descriptive tables will be produced by gender within site. The distributional properties of each variable will be examined and appropriate re-scaling undertaken, if necessary. All outliers (i.e.  $> 3$  SD's) will be identified and either verified as correct or set to missing. When possible, internal validity will be assessed by the use of bivariate scatter plots of variables known to be correlated (e.g., resting EE vs. BMI or weight vs. BP). These plots provide a useful search procedure for unanticipated outliers and/or non-linear relationships.

As in any other longitudinal study, some measurements may be unavailable in a subset of the study participants. A brief description of methods used to handle non-ignorable missing data are presented at the end of this section (cf. D.7.4)

*We describe below the analytic procedures and the power calculation, in relation to the following 4 primary hypotheses as stated in the Aims:*

- 1) AEE is negatively related to % body fat at baseline, independent of dietary intake.
- 2) AEE is negatively related to change in body weight during follow-up, independent of dietary intake.
- 3) Mean levels of AEE are negatively related to mean levels of obesity/relative weight among the populations.
- 4) Adipocytokines and hormones influence weight regulation and insulin sensitivity and interact with AEE.

[figure not shown]
#### **D.7.1.1 Weight and Body Composition are Related to AEE at Baseline**

##### **D.7.1.1.1 AEE, Weight and Body Composition**

Two measures of AEE will be available. At baseline, we will have 500 participants/site with data from the accelerometer, inclusive of those who have both DLW and accelerometer (total N, all sites = 2500; 6 days

of monitoring). We will have data generated by DLW for 75 participants/site (total N, all sites = 375). The structure of the analysis will be similar with both exposure measures.

We anticipate that data for all the primary outcomes will not conform entirely to a normal Gaussian distribution. Using BMI, PAL and AEE data collected in previous studies in Maywood (n = 567) and Nigeria (n = 735), we examined the probability distributions. A formal test statistic was performed that combines kurtosis and skewness [180] as implemented in STATA with p-values less than 0.001, suggesting deviations from normality. Kernel density estimates of the BMI, AEE, and PAL distributions are depicted in Figure 7. After applying the ladder of power approach suggested by Tukey [181], we found that BMI, AEE and PAL for both sites appear to deviate from normality. Although no transformation is preferred after application of the ladder of powers method, two potential transformations are suggested by this approach, namely  $\log X$  and  $X^{-1}$ . Tukey's approach followed by formal testing will be carried out once data on all subjects in the study has been collected and a decision about data transformations has been made. Despite the lack of normality exhibited and corroborated by the statistical tests performed, a visual exploration of Figure 7 suggests only slight deviations from normality, mostly due to well-known skewness of these distributions. Thus, we anticipate the statistical methods that make use of normally distributed data will be appropriate to analyze these data. Of course, the degree of appropriateness of these methods will depend on their robustness to deviations from normality. If it is necessary, appropriate transformations will be carried out before statistical tests are performed.

**Figure 7.** Distribution estimates of main analysis variables BMI, AEE, and PAL in two sites: Maywood (US) and Nigeria.

Following transformation of the appropriate exposure and outcome variables, Fisher's Z-transformation test will be applied in order to test hypotheses involving correlations. The resulting parametric test will be more powerful than other distribution-free approaches. The results will be corroborated by applying Spearman rank correlations and another parametric test based on the concordance coefficient introduced by Lin [182] and later extended by Chinchilli and colleagues to include repeated measures [183]. Lin's concordance correlation allows the comparison of the correlations accounting for possible differences in the mean values of the two variables under consideration. Furthermore, approximate permutation tests [184, 185] will be implemented using each of the three statistics: Pearson, Spearman and Lin's concordance, to compare agreement of the association between AEE and BMI across the three groups under investigation.

Correlation coefficients will be estimated using the Pearson correlation and confidence intervals constructed after applying the Fisher's Z-transformation. Furthermore, computer intensive statistical methods, such as bootstrapping, will be used to construct confidence intervals for both parametric and nonparametric approaches. Comparisons of these correlations will be carried out using this statistic for 1 and 2 samples [186], as well as approximate permutation tests [184, 185]. In addition, multivariate regression analysis will be fit to adjust for potential confounders. Confounders will include age, gender, and any other significant

predictors defined by the univariate analyses. Potential non-linear functions will be explored to see if they fit the data better. Sub-group analyses will be undertaken, with participants in each site divided by gender.

We have no evidence to suggest that the relationship between AEE and BMI is non-linear in the parameters. However, we will perform all our analyses using multivariate linear regression methods allowing for non-linearity of the covariates. Standard statistical methods based on the F-statistic and  $R^2$  will be used to decide the best fitting model to our data. It is anticipated that there will be more than one "best model" obtained. We will choose one based on two approaches. First, subject matter considerations will eliminate some models. Second, a computer intensive approach based on bootstrap sampling will be implemented in a fashion similar to that introduced by Sauerbrai and Schumaker [187] to aid automated variable selection.

Repeat accelerometer measures will be made in all individuals at the 2 year exam (with estimated 20% attrition, N=2000). We will use these data to assess tracking of AEE levels and identify potential cross-site variation in seasonal effects, etc. A second measure will offer important information about potential between-site heterogeneity that might help explain anomalous findings (i.e., weak or absent relationships at a particular site). If appropriate, we could also use this data in a "regression-dilution" type of analysis that corrects for the underestimation of exposure-outcome effects from "noise" in individual exposure levels.)

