**Table 5. Proposed Study Measures**

	Baseline (N)	12-Mo Follow-Up (N)	24-Mo Follow-Up (N)	Use of Data
Physical Activity				
Accelerometer	2500		2500	Exposure
DLW	375			Concordance, exposure
Questionnaire	2500			Exposures
Body Composition				
BIA	2500		2500	Outcome: baseline & change
Isotope Dilution	500		500	Calibrate BIA change data
Dietary Intake	2500			Covariate
Anthropometrics	2500	2500	2500	Outcome: baseline & change
Blood pressure	2500			Outcome
Adipocytokines/Hormones	2500			Outcome

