## D.4 Measurement Procedures

### D.4.1 Activity Energy Expenditure

Total daily EE is comprised of three components: resting EE, AEE, and thermic effect of food. In this study, we are most interested in AEE and its relationship to weight change and insulin sensitivity. AEE will be measured by two methods: accelerometers and DLW. All participants in each site will wear an activity monitor for 6-9 days, while a subset will undergo the DLW procedure as well. Our previous experience with measurement of EE indicates that both resting EE and AEE are very stable traits, with within-person correlations of 0.9 and 0.8 at intervals of 1-2 years, respectively [135]. For those participants in the DLW

[figure not shown]
subset, resting EE will be measured by indirect calorimetry, and thermic effect of food will be estimated as 10% of total daily EE. All methods are described below.

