The Actical activity monitor will be initialized for each participant on the morning of the initial clinic examination, using the on-site computer. The participant's ID, epoch period (1 minute), start date and time, and mode will be entered into the main program. Use of the activity monitor will be explained to the participant: the participant will be asked to wear the activity monitor at all times over the next 8 days, including during sleep; the only time the monitor should be removed is while bathing, showering, or swimming. The activity monitor will be placed on the participant on a belt at the waist, positioned just behind the left hip bone. The participant will be trained in proper handling of the accelerometer, including removal and placement of the monitor on the belt as well as placement of the belt on the body, in order to ensure accurate measurements. If the participant has problems sleeping with the monitor, they will be encouraged to remove it during sleep hours. An additional belt will be provided in case it gets wet and needs to be swapped out. Staff members will contact participants within 24 hours after the initiation of the monitoring session to ensure that there is no discomfort with the monitors. In addition, the monitor will be checked at the midpoint home or clinic visit to ensure proper placement and recording. On day 8, each participant will return to the clinic, and the staff member will verify end date and time and download the data. Data will be presented as activity counts per minute for the whole day and during hours the participant is awake, as well as kcal/day or METs/wk in AEE as calculated using the accompanying software [153, 155, 156, 162, 163].

Investigators at each site have significant experience with accelerometer-based activity monitors and with the validation of monitors using the DLW method. Staff will be collectively trained on the use and handling of the Actical. In addition, we will validate the Actical activity monitor for estimation of energy expenditure in AEE at each site through the comparison with DLW results. Validation of this instrument will help in future studies for the quantification of AEE at significantly lower cost than available with DLW.

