Over the years, we have had extensive experience with several models of accelerometers, activity monitors, and heart rate monitoring devices. Missing data is a well-documented problem with activity monitors in general and can result from instrument failure or non-compliance of the participant, i.e., the monitor is simply removed for part of the measurement period. In our experience, all cases of truncated data collection (which occurred in less than 2% of participants) had at least 4 days of data collected over the 7-9 day measurement period, providing at least some data for analysis. Methods of handling missing data are further discussed in the analytical section.

The consultants on this project, Drs. [name] and [name], are currently working on advanced methods of analysis for data generated from accelerometers. They have demonstrated that converting the output from accelerometry to units of acceleration (in m/s) from counts provides substantial additional information by capturing speed of motion [130]. After adjustment for built-in frequency filtering by the specific accelerometer model, acceleration is linearly associated with activity counts, as well as with EE. [name] and [name] are also developing methods using Hidden Markov Models and other mathematical approaches to improve the accuracy of accelerometer data, particularly with regard to recognition of patterns of activity that allow further differentiation among activities. The DLW data from this project will therefore help improve the accuracy of accelerometry as a tool in survey research, while improving the precision of the data collected in our project.

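### D.7 gives no method for using the concurrent DLW subset to correct accelerometer AEE. This matters chiefly for the Hypothesis 2 per-kcal slope and for the unnamed AEE measure in Hypothesis 3.

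*Combined protocol and SAP*

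**What the plan says.** - D.7.1.1.1 lists two exposures, accelerometer AEE (500 per site, 2,500 in all, including the DLW participants) and DLW AEE (75 per site, 375 in all), and says: "The structure of the analysis will be similar with both exposure measures". D.2 makes the two measurements concurrent, and the Specific Aims make the DLW group a random subset.
- Table 5 gives the use of DLW as "Concordance, exposure". For isotope dilution it gives "Calibrate BIA change data", and D.4.2.2 adds: "The ID data will be used to calibrate BIA for change in body composition within individuals over the 2-year follow-up".
- D.4.1.1 states an intent: "we will validate the Actical activity monitor for estimation of energy expenditure in AEE at each site through the comparison with DLW results". It also says that the DLW data will help accelerometry as a survey tool "while improving the precision of the data collected in our project". Neither sentence says how the values of the other 2,125 participants would change.
- The only measurement-error correction in D.7 is at the end of D.7.1.1.1. It begins "If appropriate, we could also use this data in a", goes on to a regression-dilution type of analysis, and uses the two-year repeat accelerometer data.
- The final Hypothesis 2 model (D.7.1.2) estimates the change in weight slope per unit of AEE. Its site terms are optional.
- For Hypothesis 3, D.7.1.3 regresses site mean AEE on site mean obesity, weighted by the sampling error of mean AEE. D.7.2 adds a comparison of mean AEE between the most and least obese groups. Neither place names the AEE measure.
- D.4.1 says "All methods are described below", but no DLW methods section follows in this copy. What that section may say is not known.

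**The concern.** The accelerometer is the exposure for the whole cohort, and DLW is the reference that the protocol itself relies on. Both are planned in the same 375 people, yet D.7 analyses them side by side and never links them.

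Two results are exposed. If device error is largely classical, the accelerometer slope per kcal is too small. That matters most for Hypothesis 2, where the DLW-only slope is imprecise. B.9 plans to give absence of an association a definite interpretation, so an attenuated slope could be read as a weak effect of AEE. For Hypothesis 3, device error that differs between sites would enter accelerometer means, and the planned weights do not reflect it. With no measure named, the choice between accelerometer and DLW means stays open until the data are seen.

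**Working it through.** **1. The plan's own power figures.** One-sided power is Φ(atanh(r)·√(n−3) − 1.645).
- D.7.2 states over 83% at r = −0.15 for the combined sites. With n = 300 (375 less 20% attrition) this gives Φ(2.605 − 1.645) = 83.1%. A two-sided test with n = 375 also gives 83.0%, so the text does not settle which was used. I use n = 300, because attrition applies to a change outcome.
- Hypothesis 3 at r = 0.85: 55.2% (5 points), 80.7% (effective 7) and 95.3% (10), matching the stated 55%, 80% and 95%.

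**2. Indicative size of device error** (C.2.2.1, South Africa, total EE, r = 0.6, DLW SD 655, accelerometer SD 990).
- Slope of DLW on accelerometer: 0.6 × 655/990 = 0.40. The Fisher interval for r at n = 18 is 0.185 to 0.833. With SDs fixed, the slope interval is 0.12 to 0.55.
- Mean offset: 2775 − 2600 = +175 kcal/d. SD of the difference is √(655² + 990² − 2·0.6·655·990) = 794; 95% CI −220 to +570 at n = 18.
- The section does not say whether the DLW figures are for the 18 or for all 27 people.
- Correction by repeat accelerometry alone: dividing 0.397 by the stated six-day reliability of 0.92 or 0.83 gives 0.43 or 0.48. Dividing by the 1–2 year within-person correlation of 0.8 in D.4.1 gives 0.50. Most of the indicated attenuation would remain.

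**3. Precision of the per-kcal slope.** Relative 95% margins, with ρ the true AEE–outcome correlation and r the accelerometer–DLW correlation (assumed 0.6 or 0.45):
- DLW only: 1.96·√((1−ρ²)/(n−2))/ρ.
- Calibrated: 1.96·√(a² + c²), with q = ρr, a = √((1−q²)/(N−2))/q and c = √((1−r²)/373)/r. This assumes a common calibration slope and non-differential error.

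| | DLW only | Calibrated, r = 0.6 | Calibrated, r = 0.45 |
|---|---|---|---|
| Hypothesis 2, ρ = −0.15 (n = 300, N = 2,000) | ±75% | ±50% | ±68% |
| Hypothesis 1, ρ = −0.5 (n = 375, N = 2,500) | ±17.6% | ±18.4% | ±26.3% |
| Hypothesis 1, ρ = −0.6 | ±13.5% | ±16.9% | ±24.5% |

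The Hypothesis 1 correlations are those that D.7.2 expects. The −0.15 is stated there for change in body composition and is used here for weight change.

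**4. Hypothesis 3.** Mean AEE is the dependent variable, so site-varying device error unrelated to obesity adds scatter. It biases the slope only if it covaries with site obesity.
- Illustration: take the between-site SD of true AEE as 130 to 160 kcal/d (the spread of the weight-adjusted means in Table 1) and assume a site-to-site SD of device bias b. Then r = 0.85·√(S²/(S² + b²)).
- b = 50 gives r = 0.79 to 0.81, and power at effective n = 7 of 70% to 73%. b = 100 gives 0.67 to 0.72, and 50% to 57%. b = 0 gives 81%.
- Standard error of a site mean, assumed SD 300: DLW only 300/√75 = 34.6 kcal/d. Calibrated, √(300²(1−r²)/75 + r²·300²/500) = 28.9 (r = 0.6) or 31.5 (r = 0.45).

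**5. The two devices in the preliminary data.** By the population mean BMI rows of Table 1, Maywood is highest and Nigeria lowest in both sexes. US minus Nigeria, women, AEE/kg:
- Accelerometer (Table 1, n = 20 and 18): 12.42 − 9.14 = +3.3 (95% CI 0.1 to 6.5).
- DLW (Table 3, n = 180 and 150): 10.0 − 13.5 = −3.5 (−4.6 to −2.4).

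**6. Covariates in the calibration.** If intake is in the outcome model but not in the calibration, the slope is multiplied by (1−c²)/(1−r²c²), with c the AEE–intake correlation. For assumed c of 0.3 to 0.5 this is 0.94 to 0.82 (r = 0.6) or 0.93 to 0.79 (r = 0.45).

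**The case against.** - **The intent is stated.** D.4.1.1 commits to site-level validation and ties the DLW data to precision. This stands: what is missing is the analysis method. The BIA comparison is also uneven, since its calibration is stated in Table 5 and D.4.2.2, and D.7 gives no model for it either. A method for the accelerometer may lie in the DLW text that is not in this copy.
- **DLW is already analysed alone.** For Hypothesis 1 this largely answers the point. A reader might infer that calibration improves Hypothesis 1. At the protocol's expected correlations it is less precise than DLW only (step 3). The answer does not carry over to Hypothesis 2, where DLW only is ±75%.
- **Hypothesis 3 needs no calibration.** A reader might infer that site device error biases the meta-regression slope. D.7.1.3 has AEE as the dependent variable, so that needs error that covaries with obesity. Naming DLW as the measure would settle most of the problem. But the measure is not named, and the comparison of the most and least obese groups takes in the error directly.
- **The evidence on size is thin.** A reader might take 0.40 as the attenuation to expect, or the reversal in step 5 as proof of device bias. The first is total EE in about 18 people at one site, and its offset interval includes zero. The second compares separate samples. The pilot Nigerian women had mean BMI 26.2, against 23.0 in Table 3. If the error is largely Berkson-type, attenuation would be small.
- **Much is unaffected.** Within-site correlation tests, within-site median splits, activity-count analyses and DLW-only analyses do not depend on the kcal scale of the device. D.7 does not say whether its accelerometer exposure is kcal or counts.

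**Conclusion.** The concern holds within limits. D.7 has no procedure that uses the paired DLW data to correct accelerometer AEE, and its optional correction uses the same device. The consequences are a possible attenuation of per-kcal accelerometer slopes, chiefly for Hypothesis 2, and an open choice of measure for Hypothesis 3 that can cost power or distort the comparison of extreme groups.

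The size is unknown, because the documents give no accelerometer–DLW correlation for AEE in these populations. The gain in step 3 for Hypothesis 2 rests on ρ = −0.15, on r of 0.45 to 0.6, on a common calibration slope and on non-differential error. Site-specific slopes would widen the calibrated margins. The documents do not support saying that the planned tests are invalid, that the bias is of known size, or that the protocol has no validation plan. It is a worthwhile change at low cost, held with moderate confidence.

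**What to change.** 1. **Hypothesis 3:** name the AEE measure and its scale (kcal/d or kcal/kg/d). Use DLW or DLW-anchored site or site-by-sex means in both the meta-regression and the comparison of the most and least obese groups, with standard errors that include calibration error.
2. **Hypothesis 2:** pre-specify regression calibration of accelerometer kcal AEE from the 75 DLW participants per site.
   - Use site-specific intercepts, and site-specific slopes if they differ.
   - Use exactly the covariates of the outcome model, including intake. Include weight only if the outcome model does. For intake, use the same two recalls as in the rest of the cohort, since D.4.4 gives the DLW subset three.
   - Bootstrap both stages, include site terms in pooled models, and report the result beside the uncalibrated and DLW-only slopes.
3. **Hypothesis 1:** keep DLW only as the reference per-kcal slope, and report the calibrated slope as a sensitivity analysis.

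The cost is SAP text and programming; all the data are already planned. The downsides are wider intervals than the uncalibrated analysis and reliance on non-differential device error. If the full DLW methods section already holds such a model, a cross-reference from D.7 would be enough for the calibration part.
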